## 9 METHODS: DATA COLLECTION, MANAGEMENT AND ANALYSIS

---

### 9.1 DATA COLLECTION

Outcomes are assessed using different sub-studies, including cohort studies, continuous household surveys, passive clinic- and CHV-based surveillance and ethnographic and economic studies; for an overview, see Section 5, Objectives and outcomes, page 15. The details of each of these components are outlined below.

#### 9.1.1 COVID-19 mitigation efforts

As a result of the COVID-19 pandemic, the Government of Kenya and the KEMRI SERU have developed guidelines to be followed within research trials to protect participants and study staff from SARS-CoV-2 transmissions (KEMRI-SERU section 3.2.5, Ref: KEMRI/SERU/REC/GUIDE/001 of 22nd June 2020). These mitigation efforts are periodically updated by the Ministry of Health and KEMRI. We will adhere to the prevailing Ministry of Health and KEMRI guidelines at the time that the study commences and will adopt any new recommendations during the course of the trial.

#### 9.1.2 Cohort study to assess the incidence of clinical malaria

Households with participants aged 1 to <15 years of age will be randomly chosen from the household in the census database. A single resident aged 1 to <15 years will be selected from these households to be enrolled in the cohort. They will be followed for up to 6.5 months, including two weeks of lead-in time for parasite clearance and six months of subsequent follow-up, contributing to the analysis person time). The sampling frame of households may be updated based on findings from subsequent routine CHV censuses in the study area. A baseline cohort study will be conducted before the deployment of ATSB to inform the restricted randomisation, followed by a cohort study, to assess the impact of ATSB. The procedures in these cohorts will be similar, as outlined below.

##### 9.1.2.1 *At recruitment/enrolment*

- Informed consent will be administered to the parent/caregiver, and assent to the participant if he/she is 13-<15 years of age
- A fingerprick blood sample (~250µL or 1mL) will be collected to perform an RDT and to prepare approximately five dried blood spots (DBS) on filter paper for subsequent molecular and potentially serological testing and for evaluation of mosquito salivary antigens
- All cohort members will be treated with artemether-lumefantrine (AL; first-line antimalarial in Kenya) irrespective of their RDT result to clear any subpatent infections that may exist
- A questionnaire will be administered to the head of the household to assess household assets for the construction of socio-economic status (SES) categories and to assess household malaria control measures (e.g. number of LLINs, housing construction)
- A questionnaire will be administered to the parent/caregiver and/or the participant to assess activities of interest, including medical and vaccination history, medication use, inclusion in other clinical trials, care-seeking behaviour, LLIN use, daily commuting and travel information, and information about the structure that the participant sleeps in
  - A photograph will be taken of vaccination history and pertinent medical records from the maternal child health booklet or other records

- For participants enrolled in the HDSS or clinical studies, we will link the cohort data to their study/HDSS records
- For young women of childbearing age (12-14 years), pregnancy status will be evaluated in a private and confidential location through the following algorithm:
  - If the woman has had menarche, her last menstrual period was  $\geq 6$  weeks ago, and if she has any suspicion that she may be pregnant, then she will be offered a urine pregnancy test
  - If she declines or is found to be pregnant, she will be considered ineligible for the cohort
- A photograph may be taken of the participant to create a study identification badge that the participant will keep for identification by study staff for scheduled and sick visits

9.1.2.2 *Parasite clearance confirmation visit (2 weeks after enrolment)*

- Before this visit, the study team will call the cohort member to remind them of the upcoming visit and reschedule if necessary. Up to three visit attempts will be made to complete the parasite clearance confirmation visit.
- Two weeks after the enrolment visit, the household will be visited and a finger-prick blood sample (~250 $\mu$ L to 1mL) will be drawn to prepare five dried blood spots, and to prepare a blood smear for parasite clearance confirmation.
- If the participant is febrile at this visit, the staff member will review the RDT result from the enrolment visit.
  - If the enrolment visit RDT was negative, the participant will be re-tested with an RDT and if positive, the participant will be ineligible for the cohort and second-line antimalarial treatment will be administered as per national guidelines (e.g. dihydroartemisinin-piperaquine). If the RDT administered during this visit is negative, we will proceed with the blood smear.
  - If the enrolment visit RDT was positive, the blood smear will be expedited.
- If the participant is found to be positive for malaria by microscopy, we will consider the participant ineligible for the cohort and will withdraw him/her. A staff member will return to the house to convey this information and provide second-line antimalarial treatment as per national guidelines (e.g. dihydroartemisinin-piperaquine).

9.1.2.3 *At each monthly cohort visit (starting 4 weeks after enrolment)*

- Prior to each follow-up visit, the cohort study team will call cohort members to remind them of the next visit and reschedule, if necessary, to minimize loss to follow-up. Up to three visits will be made to each cohort study household to complete a follow-up visit.
- At each of these visits, a finger finger-prick blood sample (~250 $\mu$ L to 1mL) will be drawn to prepare approximately five dried blood spots for testing, as indicated in the enrolment visit.
- If the participant has an axillary temperature of  $\geq 37.5^{\circ}$  C or reported history of fever in the last 48 hours, a malaria RDT will be performed using blood from the same fingerprick. Those who test positive for malaria by RDT will be treated at the household according to the Kenya Ministry of Health Guidelines unless they already received appropriate antimalarial treatment from other sources in the previous seven days. Cohort members who do not have objective fevers or report a history of fever in the last 48 hours will not be tested for malaria by RDT.
- For women of childbearing age, pregnancy status will be evaluated as described in the enrolment visit section. Those in whom a pregnancy test is indicated but who decline and those who have a positive pregnancy test will be withdrawn from the cohort. These women

may opt to be visited and evaluated for malaria, free of charge for the duration that they would have been in the cohort.

- A questionnaire will be administered on a tablet or smartphone to the participant or his/her parent/guardian, including questions about the history of recent illness (including AEs and SAEs), care-seeking, LLIN use, and travel and commuting history. If the cohort member sought care between scheduled visits, we will copy any relevant information from these health records to evaluate any malaria diagnostics performed and antimalarial treatment given
- A follow-up visit in four weeks time may be scheduled at this time. Parents/guardians and the participant will be reminded to call the study staff at the number provided on the consent form if the participant becomes ill before the next scheduled visit.
- The limited care provided by the study team includes any care related to study procedures, malaria illness, or other uncomplicated acute illnesses such as acute respiratory or gastrointestinal disease. The study will not be responsible for the care of pre-existing conditions or chronic or traumatic conditions diagnosed during the trial.

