	
Eligibility criteria for participants in the cohort study
 
 
• Inclusion criteria cohort 
 
○ A resident of a household within the core area of a study cluster, defined as living in the household in the recent four months and planning to live in the same household for the next 6.5 months
 
○ Aged <math>\geq 1</math> year and <math>< 15</math> years at the time of enrollment
 
○ Written informed consent and/or assent
 
 
 
• Exclusion criteria cohort 
 
○ A confirmed or suspected pregnancy. Pregnant women are excluded because they are eligible for intermittent preventive treatment of malaria in pregnancy (IPTp).
 
○ Taking daily cotrimoxazole prophylaxis (because this has antimalarial effects)
 
○ Known sickle cell disease (because they received antimalarial prophylaxis)
 
○ Contraindication to artemether-lumefantrine, the medication used for parasite clearance
 
 
 
 
Eligibility criteria for households for ATSB deployment
 
 
• Inclusion criteria 
 
○ Households located within one of the 40 clusters (core or buffer area) randomly allocated to the trial intervention arm with a least one permanent resident
 
 
 
• Exclusion criteria 
 
○ Refusal of consent by the head-of-household to deploy ATSB on the outer walls (intervention villages only)
 
○ Vacated compounds
 
 
 
 
Eligibility criteria for households for entomological monitoring
 
 
• Inclusion criteria households for entomological monitoring 
 
○ Household located within the core area of the cluster
 
○ Head of household or his/her representative is at least 18 years of age
 
○ Written informed consent for the collection of entomological data by the head of household or representative
 
 
 
• Exclusion criteria households for entomological monitoring 
 
○ No residents sleeping in the household during the planned night of monitoring
 
 
 
 
Eligibility criteria for human landing catches
 
 
• Inclusion criteria human landing catches 
 
○ Men aged 18 to 49 years
 
○ Willingness and ability to work late at night for up to 7 hours at a time
 
○ Willingness to take and tolerate a treatment regimen of the appropriate Kenya Ministry of Health (MoH) recommended antimalarial and chemoprophylaxis with 250 mg of mefloquine weekly to prevent malaria starting two weeks before the start of and until four weeks after completing HLCs
 
○ Written informed consent
 
 
 
• Exclusion criteria human landing catches 
 
○ Refusal/inability to work late at night for up to 7 hours at a time
 
○ Unwillingness to take or intolerance/allergy to appropriate MoH treatment regimen or chemoprophylaxis
 
 
 
 
Eligibility criteria for participants in rapid ethnographic methods evaluation (community members)
 
 
• Inclusion criteria ethnographic evaluation (community) 
 
○ A resident of a household within an intervention area defined as an ATSB area during the main trial or an ASB area during any preliminary studies
 
○ Resides in a household at the time of ASB/ATSB deployment, where the ASB/ATSB was installed for at least one month.
 
○ 18 years of age or older if participating in focus group discussions; 15 years of age or older if participating in in-depth interviews
 
 
 
• Exclusion criteria ethnographic evaluation (community) 
 
○ Unable to provide consent
 
 
 
 
Eligibility criteria for participants in rapid ethnographic methods evaluation (ATSB monitoring assistants)
 
 
• Inclusion criteria ethnographic evaluation (ATSB monitoring assistants) 
 
○ Serving as an ATSB monitoring assistant with experience installing ATSBs and monitoring the deployment
 
 
 

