#### 6.3.3.1 Cohort study (active case detection)

Participants aged 1 to <15 years who are usual residents of households within a core area of a study cluster will be randomly selected for enrolment into an active cohort (see section 9.1.2, Cohort study to assess the incidence of clinical malaria, page 34). All consented and enrolled cohort members will be given a presumptive treatment course of artemether-lumefantrine to clear any malaria infections. Parasite clearance will be confirmed two weeks after treatment. The scheduled monthly cohort visits will begin one month after the first day of this treatment. During monthly visits, study staff will collect a fingerprick (or heel prick in small infants) blood sample (about 250uL to 1 ml) for dried blood spots on filter paper. Should the cohort member report a fever in the last 48 hours or have an axillary temperature of  $\geq 37.5^{\circ}\text{C}$  at the time of the visit, the study staff member will perform a malaria RDT, and if positive, will treat the participant as per the Kenya Ministry of Health guidelines. A questionnaire will be administered to all cohort members and/or their caregivers to assess for illness, care-seeking, and LLIN usage, among other indicators. Several questions will be asked to monitor for any SAEs. A questionnaire assessing ATSB knowledge, attitudes and perceptions (KAP) will also be administered. Please see section 9.1.7, Rapid ethnographic methods, page 39, for more details.

Figure 4: Overview of activities and procedures in intervention and control areas

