### 11.2.4 Inclusion of vulnerable subjects: children and pregnant women

The cohort study will include children age 1-15 years. Informed consent from the parent or guardian will be obtained before participants are enrolled. Additional assent will be obtained for children age 13-15 years (see 11.2.5, Consent procedures, below) per local guidelines.

Pregnancy is an exclusion criterion because enrolment in the cohort requires presumptive clearance of any existing infections with artemether-lumefantrine. WHO does not yet recommend artemether-lumefantrine for the case-management of confirmed malaria in the first trimester, nor does it recommend the presumptive treatment with ACTs at any time during pregnancy. It is possible that some girls aged 12-15y could be pregnant. Pregnancy will be excluded by asking girls aged 12-15y about their date of last menstrual period. If this is  $\geq 6$  weeks, she will be asked if she could be pregnant. If she is unsure, a urine human Chorionic Gonadotropin (hCG) rapid pregnancy test will be offered. Any girl who is unsure about her pregnancy status and is hesitant to do a urine-based hCG pregnancy test will not be eligible for enrolment. Any study participant who is pregnant at screening or becomes pregnant during the study will be referred to the antenatal clinic for further follow-up and care.

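### Pregnancy screening before presumptive artemether-lumefantrine acts on suspicion only when the last period was at least 6 weeks ago, although the cohort excludes any suspected pregnancy

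*Protocol*

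**What the plan says.** **The criterion.** The cohort exclusion list in Section 7.3.2.2, repeated in the trial registration table in Section 2, begins with "A confirmed or suspected pregnancy". Suspicion alone is enough, whatever the date of the last period.

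**The enrolment steps.** Section 9.1.2.1 sets out an algorithm for girls aged 12 to 14, carried out in private. Three conditions must all hold. Two are menarche and an interval of 6 weeks or more since the last period; the third, with the action that follows, reads "and if she has any suspicion that she may be pregnant, then she will be offered a urine pregnancy test". The only routes to ineligibility in the algorithm are refusing that test or being found pregnant.

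**The ethics section.** Section 11.2.4 states: "Pregnancy will be excluded by asking girls aged 12-15y about their date of last menstrual period". If the answer is 6 weeks or more, "she will be asked if she could be pregnant", and a urine test follows if she is unsure.

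**The treatment.** Section 6.3.3.1 says: "All consented and enrolled cohort members will be given a presumptive treatment course of artemether-lumefantrine". Section 9.1.2.1 agrees, "All cohort members will be treated with artemether-lumefantrine", and makes the course independent of the RDT result.

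**The reason given.** Section 11.2.4 ties the exclusion to this presumptive course. According to that section, the drug does not so far have WHO's backing "for the case-management of confirmed malaria in the first trimester". On presumptive use its account of WHO's position is broader: "nor does it recommend the presumptive treatment with ACTs at any time during pregnancy". (Section 7.3.2.2 gives a different reason, eligibility for IPTp.)

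Section 9.1.2 applies similar procedures to the baseline cohort. Section 9.1.2.3 reuses the same pregnancy algorithm at monthly visits, the first of which is 4 weeks after enrolment.

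**The concern.** The eligibility rule and the steps that put it into practice do not match. The rule excludes on suspicion. The steps ask about suspicion, or act on it, only behind a 6-week threshold. A girl below the threshold who thinks she may be pregnant meets the exclusion, but no written step brings this out.

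What is at stake is participant safety in minors. The drug is given presumptively, so there is no confirmed infection to weigh against a risk to a pregnancy. A pregnant girl whose last true period was less than 6 weeks ago is in the first trimester, the period in which Section 11.2.4 says the drug is not yet recommended even as treatment of confirmed malaria.

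**Working it through.** No sample-size, power or error-rate figure bears on this point. The check sets the texts side by side and then works through the visit schedule.

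**Step 1: outcomes for a post-menarche girl under the written steps (Sections 9.1.2.1 and 11.2.4)**

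| Last period | Suspects pregnancy | Asked? | Result of the written steps | Section 7.3.2.2 criterion |
|---|---|---|---|---|
| at least 6 weeks ago | yes | yes | test offered; excluded if declined or positive | excluded on suspicion |
| at least 6 weeks ago | no | yes | enrolled and treated | eligible |
| under 6 weeks ago | yes | no | enrolled and treated unless she volunteers it | excluded on suspicion |
| under 6 weeks ago | no | no | enrolled and treated | eligible |

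The third row is the gap: the criterion excludes the girl, but the steps let her through to treatment.

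**Step 2: is a recent last period enough to rule pregnancy out?** Not throughout the window. The protocol gives no cycle length. Assuming 4 weeks (range 3 to 5), a period may already be late by up to 6 − 4 = 2 weeks (range 6 − 5 = 1 to 6 − 3 = 3 weeks) while she is still below the threshold.

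**Step 3: can the monthly check catch it in time?** Let *w* be the weeks since the last period at enrolment, with *w* < 6 and no further period. Monthly visit *k* takes place 4*k* weeks after enrolment if visits are on schedule, so the weeks since the last period are then *w* + 4*k*. The threshold requires *w* + 4*k* ≥ 6.

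- If 2 ≤ *w* < 6, then *w* + 4 ≥ 6, so the threshold is first met at visit 1, 4 weeks after the enrolment dose.
- If *w* < 2, then *w* + 4 < 6 but *w* + 8 ≥ 8, so it is first met at visit 2, 8 weeks after the dose.

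For every *w* < 6 the threshold is first met after the dose. Meeting it is not the same as detection, because the algorithm still requires suspicion. The monthly check can shorten the time a pregnancy stays unrecognised, but it cannot prevent the exposure.

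**Step 4: is there another check in between?** The parasite-clearance visit at 2 weeks (Section 9.1.2.2) lists no pregnancy check, although it can lead to second-line treatment, with dihydroartemisinin-piperaquine named as the example.

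**The case against.** **The criterion and the algorithm do different jobs.** Section 7.3.2.2 decides eligibility and Section 9.1.2.1 decides who is offered a test, so a girl who states a suspicion is excluded at any interval. This is right, and it limits the point to suspicion that is not voiced. It does not close the gap, because a safety exclusion in girls of 12 to 14 should not depend on unprompted disclosure.

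**Other screening might bring it out.** Section 11.2.5.1 mentions an initial eligibility screen before full consent, and Section 9.1.2.1 a medical-history questionnaire. The forms and consent pages are not available here and might ask about pregnancy. This remains possible. But neither text mentions pregnancy, and Section 11.2.4 states specifically how pregnancy will be excluded. The sentence there about a girl who is unsure and hesitant to be tested has no explicit time limit, but it follows from a test offer made only above the threshold.

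**The 6-week threshold is proportionate.** It keeps a sensitive question to girls with a late period, and an early urine test is unreliable. That is a fair reason to delay the test. It is not a reason to omit the question, since the criterion excludes on suspicion without a test, and menarche and last period are already asked about in private.

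**The group is small and its size is not quantified, and self-report stays central.** Both are true. A girl with a late period who declares no suspicion is also untested and treated, and the proposed change leaves that as it is.

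**Conclusion.** The concern holds. As written, the screening steps in Sections 9.1.2.1 and 11.2.4 are narrower than the protocol's own exclusion of suspected pregnancy. They leave a post-menarche girl with a last period under 6 weeks ago unasked before she receives presumptive artemether-lumefantrine.

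The size cannot be derived from the document. The affected group is girls aged 12 to 14, after menarche, with a recent last period and a suspicion they do not volunteer, and only some of them would be pregnant. It is probably small, and no rate is assumed here. Power and the primary analysis are not affected.

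The conclusion rests on reading the steps as complete, that is, on no form outside the protocol asking the question. The 4- and 8-week timings assume visits on schedule and no further bleeding. The first-trimester statement assumes that the reported last bleed was a true period. This is a safety inconsistency that should be corrected; it does not threaten the trial's validity.

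**What to change.** In Sections 9.1.2.1 and 11.2.4, before the enrolment dose, ask every post-menarche girl in private whether she could be pregnant, whatever the date of her last period. Then:

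- **Yes or unsure, last period at least 6 weeks ago:** offer the urine test as planned; she is ineligible if she declines or tests positive.
- **Yes or unsure, last period under 6 weeks ago:** apply the Section 7.3.2.2 criterion directly. She is ineligible, or enrolment and dosing are deferred until pregnancy can be reliably excluded. An early negative test should not clear her.

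Align the monthly check in Section 9.1.2.3 with this, and carry it into the baseline cohort procedures.

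The cost is wording in three sections and one question on the electronic form. The downside is that a sensitive question goes to more girls, with a few more tests, deferrals or exclusions. Table 7 in Section 11.3.1.3 already lists inadvertent pregnancy disclosure as a cohort risk, and Section 9.1.2.1 already requires a confidential setting.

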#### 9.1.2.4 Sick visits (participant initiated visits occurring between scheduled monthly visits)

- Study staff will tend to cohort participants for sick visits as described above
- During these sick visits, study staff will administer a “sick visit” questionnaire including questions about current illness and any associated care-seeking behaviour or medications ingested.
- Questions about physical interaction with or ingestion of ATSBs will also be included for AE and SAE monitoring.
- Will collect a finger- or heel-prick to collect 250 µL to 1 mL of blood to prepare approximately five dried blood spots on filter paper and for any other diagnostic tests that are clinically indicated based on the participant’s presentation
- In the setting of identifying that a cohort member sought care from outside of the study (identified either from a phone call or subsequent scheduled visit), study staff will attempt to gather records from the facility, CHV or pharmacy where the cohort member sought care

PCR and serological testing of the DBS specimens collected during the study will not be used for care.

